8.4.6 Treatment compliance

The assessment of patients' compliance to IMP administration is not required as the investigational drug is infused at site by the Investigator.

8.4.7 Dosage modification and management of infusion toxicities

No dose adjustment is allowed.

The following instructions are provided for the management of infusion toxicities:

Toxicity	CTCAE v.4.03 Grade (duration)	Occurrence	Action on MEN1112 infusion	Action for toxicity
Cytokine release storm and/or Tumor lysis syndrome	3 (≤7 days)	First (during " ramp-up " administration)	 Interrupt MEN1112 until resolved to grade 0, then: If ≤20% of the ramp-up infusion dose (i.e. ≤50 mL of the total 250 mL infusion solution) was missed, restart MEN1112 at the next scheduled study drug administration. If >20% (i.e. >50 mL of the total 250 mL infusion solution) of the ramp-up infusion was missed, as soon as feasible (upon resolution to grade 0) restart MEN1112 to complete the residual ramp-up dose (e.g. if the dose was interrupted when 120 mL of the second ramp-up dose had been administered, complete the second ramp-up dose on the day after). If the infusion cannot be completed within 24 hours from dilution, a new infusion solution shall be prepared. If applicable, postpone the next scheduled study drug administration (i.e. the first infusion of the following 3-day ramp-up 	 Tumor lysis syndrome (TLS)¹: Consider multidisciplinary approach with involvement of nephrologists and intensive care physicians. Potassium must not be added to the hydration fluid. In the absence of contraindications, it is recommended rasburicase at a dose of 0·2 mg/kg/day (duration determined according to the clinical response) Symptomatic hypocalcaemia is recommended to be treated with a short infusion of calcium gluconate In patients with potassium levels ≥6 mmol/l or with ≥ 25% increase from baseline, cardiac monitoring is recommended Intractable fluid overload, hyperkalaemia, hyperuricaemia, hyperphosphataemia or

Confidential

Toxicity	CTCAE v.4.03 Grade (duration)	Occurrence	Action on MEN1112 infusion	Action for toxicity
			dosing) to ensure an interval of 5 days between any study drug administration is guaranteed.	hypocalcaemia are indications for renal dialysis.
				• Consider intensive care unit admittance for severe (grade 3-4) TLS cases
				Cytokine release storm ² : paracetamol and high dose steroids (dexamethasone) are recommended. Consider intensive care unit admittance for severe (grade 3-4) cases
				Disseminated intravascular coagulation (DIC) ³ :
				• In patients with DIC and active bleeding, it is recommended the use of platelet transfusion to maintain the platelet count above 50x10 ⁹ /L
				• In patients with DIC and active bleeding, it is suggested transfusion of fresh frozen plasma (15–30 mL kg-1) with careful clinical monitoring to decide on dose adjustments.
	3 (≤7 days)	First (during "one shot" administration)	 Interrupt MEN1112 until resolved to grade 0, then: If ≤20% of the infusion (i.e. ≤50 mL of the total 250 mL infusion solution) dose was missed, restart MEN1112 at the next scheduled study drug administration. If >20% (i.e. >50 mL of the total 250 mL 	• In actively bleeding cases with persistently low fibrinogen values (below 1.5 g L-1) despite these supportive measures, it is suggested transfusion of two pools of cryoprecipitate (whenever available) or fibrinogen concentrate

Confidential

Page 82 of 132

Toxicity	CTCAE v.4.03 Grade (duration)	Occurrence	Action on MEN1112 infusion	Action for toxicity
			infusion solution) of the infusion was missed, as soon as feasible (upon resolution to grade 0) restart MEN1112 to complete the residual dose (e.g. if the dose was interrupted when 120 mL had been administered, complete the dose with 130 mL of infusion solution). If the infusion cannot be completed within 24 hours from dilution, a new infusion solution shall be prepared. If applicable, postpone the next scheduled study drug administration to ensure an interval of 7 days between any study drug administration is guaranteed.	 Routine use of tranexamic acid is not recommended. If therapy-resistant bleeding dominates the picture in hyperfibrinolytic DIC, tranexamic acid may be considered It is recommended regular clinical and laboratory surveillance of the patient, to detect the development of complications including organ failure, and to ensure the underlying condition is being adequately treated
	3 (≤7 days) 3 (>7 days) 4 (any)	Second Any Any	Discontinue MEN1112 permanently	 Consider intensive care unit admittance for severe (grade 3-4) cases
Elevated transaminase(s), disseminated intravascular coagulation, and/or other clinically	3 (≤7 days)	First	Interrupt MEN1112 until the toxicity improves to grade ≤1, then follow the instructions provided above for grade 3 cytokine release storm/tumor lysis syndrome lasting ≤7 days at the first occurrence (either during ramp-up or one shot administration, as applicable).	 Infusion related reaction (IRR)⁴: Stop the administration of medication Maintain the i.v. access and assess the patients level of consciourness
relevant (as determined by treating physician) adverse reactions	3 (≤7 days) 3 (>7 days) 4 (any)	Second Any Any	Discontinue MEN1112 permanently	 Position: - In the case of hypotension, the patient should be placed in the Trendelenburg position In the case of respiratory distress, sitting up If
Any	2	Any	Interrupt MEN1112 until the toxicity improves to grade ≤1, then follow the instructions provided above for grade 3 cytokine release storm/tumor lysis	 Administrate oxygen, if needed

Confidential

Page 83 of 132

Toxicity	CTCAE v.4.03 Grade (duration)	Occurrence	Action on MEN1112 infusion	Action for toxicity
		Anu	syndrome lasting ≤7 days at the first occurrence (either during ramp-up or one shot administration, as applicable)	• In case of anaphylaxis:
Any		Any	At Investigator's discretion, either continue the scheduled infusion or interrupt it until the toxicity is resolved; in this latter case follow the instructions provided above for grade 3 cytokine release storm/tumor lysis syndrome lasting ≤7 days at the first occurrence (either during ramp-up or one shot administration, as applicable).	 It is recommended to administer adrenaline (0.01 mg/kg intramuscularly); this can be repeated every 5–15 min. Failure of a prompt response should be followed by administration of i.v. adrenaline Fluid resuscitation: a rapid infusion of 1–2 litres of normal saline at a rate of 5–10 mL/kg in the first 5 min is recommended. Vasopressors: dopamine (400 mg in 500 mL of 5% dextrose water) administered at 2–20 mg/kg/min and titrated to increase systolic blood pressure might be required if adrenaline and fluid resuscitation have failed to alleviate hypotension. Vasopressin and norepinephrine may also be used in anaphylaxis that is unresponsive to adrenaline Antihistamines: the combined use of H1 and H2 antagonists is superior to the use of either alone. Diphenhydramine (1–2 mg/kg or 25–50 mg) may be given slowly i.v. in combination with ranitidine (50 mg) i.v. over 5 min Corticosteroids: effective in preventing biphasic reactions, but not critical in the management of anaphylaxis. If given, the

Confidential

Toxicity	CTCAE v.4.03 Grade (duration)	Occurrence	Action on MEN1112 infusion	Action for toxicity
				dosing of i.v. corticosteroids is recommended to be equivalent to 1–2 mg/kg of (methyl)prednisolone every 6 h ο For bradycardia, it is recommended atropine 600 μg i.v.
				Elevated transaminases: it is recommended to rule out possible alternative/contributing causes. For grade 3 or 4 events, monitoring of liver function tests is recommended to be carried out on a daily basis.

¹Adapted from Coiffier et al, J Clin Oncol. 2008 Jun 1;26(16):2767-78 and from Jones et al, Br J Haematol. 2015 Jun;169(5):661-71

² Adapted from Frey and Porter, Hematology Am Soc Hematol Educ Program. 2016 Dec 2;2016(1):567-572

³ Adapted from Thachil et al, J Thromb Haemost2015;13: 671–5.

⁴ Adapted from Rosellò et al, Ann Oncol (2017) 28 (suppl 4): iv100-iv118

In case an infusion is interrupted due to drug-related toxicities (not meeting permanent treatment withdrawal criteria), when the infusion is resumed and/or at all subsequent infusions, the infusion duration shall be prolonged to 8 hours (total infusion time), using a constant infusion rate. In case of grade 3 or 4 Cytokine Release Syndrome (CRS), it is recommended to consider the use of high dose corticosteroids. Intensive-care supportive therapy should be considered for severe or life-threatening CRS, tumour lysis syndrome and/or disseminated intravascular coagulation.

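### The dopamine rate in the anaphylaxis guidance (2–20 mg/kg/min) cannot be delivered from the stated bag; the unit is probably wrong and likely should be µg/kg/min

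*Combined protocol and SAP*

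**What the plan says.** Section 8.4.7 introduces its table with "The following instructions are provided for the management of infusion toxicities". In the column on action for toxicity, the anaphylaxis guidance lists adrenaline, then fluids, then vasopressors.

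- **Fluids:** "a rapid infusion of 1–2 litres of normal saline at a rate of 5–10 mL/kg in the first 5 min is recommended".
- **Dopamine:** "dopamine (400 mg in 500 mL of 5% dextrose water) administered at 2–20 mg/kg/min", titrated to systolic blood pressure. It "might be required if adrenaline and fluid resuscitation have failed to alleviate hypotension". Vasopressin and norepinephrine are named as other options.
- **Source:** footnote 4 says the infusion-reaction text is adapted from a published guideline.

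No other part of the protocol gives a dopamine dose or corrects this one.

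**The concern.** The cell gives both a bag strength and a weight-based dose rate, and together they fix the volume that must be infused. That volume looked too large for a drug that is to be titrated against blood pressure. If the printed unit is mg where µg was intended, the instruction overstates the dose 1000-fold, in guidance written for a hypotensive emergency.

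Infusion reactions are common in this trial. Section 6.2.4.2 reports treatment-related infusion reactions below grade 3 in 38.3% of patients on the one-shot schedule, and treatment-related events leading to temporary interruption of dosing in 63.8%. Sites will therefore consult this table. These figures do not say how often a vasopressor would be needed. The documents give no such frequency, so the number of patients exposed to the error cannot be estimated.

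**Working it through.** The protocol states no volume rate for dopamine, so there is no derived figure to reproduce. The check is unit arithmetic on figures from the one table cell.

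**Inputs (section 8.4.7)**
- Dopamine bag: 400 mg in 500 mL
- Dopamine dose rate: 2–20 mg/kg/min
- Rapid saline: 5–10 mL/kg in the first 5 min

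**Step 1. Concentration:** 400 / 500 = 0.8 mg/mL.

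**Step 2. Volume rate = dose rate / concentration**
- Low: 2 / 0.8 = 2.5 mL/kg/min
- High: 20 / 0.8 = 25 mL/kg/min

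**Step 3. Saline rate = volume / time**
- Low: 5 / 5 = 1 mL/kg/min
- High: 10 / 5 = 2 mL/kg/min

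**Step 4. Comparison, independent of body weight**
- Lowest dopamine against fastest saline: 2.5 / 2 = 1.25
- Low against low: 2.5 / 1 = 2.5
- High against high: 25 / 2 = 12.5

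Every dopamine rate in the stated range exceeds every saline rate.

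**Step 5. Time to empty one bag.** As written, time = 400 mg / (rate × weight). With µg/kg/min, flow in mL/h = rate × weight / 1000 / 0.8 × 60, and bag time = 500 / flow. The weights are assumptions.

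| Assumed weight | As written, at 2 / 20 mg/kg/min | With 2 / 20 µg/kg/min: flow | With 2 / 20 µg/kg/min: bag time |
|---|---|---|---|
| 40 kg | 300 s / 30 s | 6 / 60 mL/h | 83 h / 8.3 h |
| 70 kg | 171 s / 17 s | 10.5 / 105 mL/h | 48 h / 4.8 h |
| 120 kg | 100 s / 10 s | 18 / 180 mL/h | 28 h / 2.8 h |

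Worked at 70 kg as written: 2 × 70 = 140 mg/min, and 400 / 140 = 2.86 min = 171 s. With µg: 2 × 70 / 1000 / 0.8 × 60 = 10.5 mL/h, and 500 / 10.5 = 47.6 h.

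**Step 6. Could the unit be a reading fault?** The microgram sign survives later in the same guidance ("it is recommended atropine 600 μg i.v") and in the uric acid threshold in Appendix I, section 2. This makes a lost µ less likely but does not exclude it.

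**The case against.** The strongest objection is that the point rests on one character in text a program read from a PDF, and a reading fault is not an error in the plan. The surviving microgram sign in the atropine line is only partial reassurance. A page break separates that line from the dopamine line, and the same reading garbles the potassium unit in Appendix I, section 4, while rendering the calcium unit there correctly. This stands: the printed page has to be seen before anything is changed, and confidence cannot go above medium.

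Second, the documents show that mg/kg/min is unworkable but do not state the intended unit, and the guideline in footnote 4 was not available. This also stands, so µg/kg/min is an inference from the bag strength.

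Third, the practical weight is limited. Dopamine is advised only after adrenaline and fluids have failed, and alternatives are named. Patients are in hospital for at least 24 hours after each Cycle 1 administration visit (section 8.4.5). The volumes make literal delivery unlikely. All of this is fair, and it places the point below a design or analysis fault. It does not justify leaving a wrong dose unit in emergency instructions, particularly when section 5.7 requires the protocol's instructions to be followed exactly.

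**Conclusion.** The concern holds for the text as it reads. The bag and dose rate in section 8.4.7 together require 2.5–25 mL/kg/min, above the 1–2 mL/kg/min set for rapid fluid resuscitation in the same cell, so the infusion cannot be titrated. This result needs no assumption about body weight. The bag times and pump rates rest on assumed weights of 40–120 kg.

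The likely intended unit is µg/kg/min, which would make the stated dose 1000 times too high. That reading is inferred from the workable flow it gives, with medium confidence.

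The point should be fixed because it concerns a dose in operative safety instructions. It has no bearing on the endpoints, the DLT rule, dose escalation or any analysis.

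**What to change.** 1. Check whether the printed page of section 8.4.7 says mg or µg. If it says µg, no change is needed.
2. If it says mg, check the dopamine rate against the guideline named in footnote 4.
3. Subject to that check, change the rate to 2–20 µg/kg/min and notify the sites.

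The edit is one line and does not touch design, data or analysis. Because it bears on patient safety, section 5.7 may class it as a substantial amendment needing ethics committee and competent authority approval. It could be bundled with the next amendment, with sites told of the correction in the meantime.

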8.4.8 Concomitant Medication

During the study, patients are not allowed to receive:

- Any other investigational agent.
- Any active agent in AML setting (hydroxyurea is allowed throughout the whole duration of the first induction cycle in case of need for WBC count reduction).

Concomitant and prior (i.e. within 30 days before enrolment) medications shall be carefully checked since the use of the above reported medications may represent an exclusion criterion and make the patient ineligible to participate in the study. Furthermore, the regular and occasional use of any concomitant medication has to be recorded starting from Screening until the End of Study Visit.

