6.2.4.1 Patient disposition and reasons for withdrawal

As of 28 March 2019 (data cut-off date, unclean data) a total of 57 patients have been screened in the ARMY-1 study, 47 of whom have been treated, all using the "*one-shot*" schedule of administration, as tabulated below. Patient disposition at the cut-off date is provided below:

Number of Patients	Cohort 0.1 mg/kg N=4	Cohort 0.3 mg/kg N=7	Cohort 0.6 mg/kg N=6	Cohort 1.0 mg/kg N=8	Cohort 1.7 mg/kg N=17*	Cohort 2.5 mg/kg N=5	Overall N=47
Screened	7	8	7	10	20	5	57
Screening failure	3	1	1	2	3	0	10
Safety population	4/(100.0%)	7/(100.0%)	6/(100.0%)	8/(100.0%)	17/(100.0%)	5/(100.0%)	47/(100.0%)
DLT population	3/(75.0%)	6/(85.7%)	6/(100.0%)	7/(87.5%)	7/(41.2%)	5/(100.0%)	34/(72.3%)
Efficacy population	2/(50.0%)	4/(57.1%)	5/(83.3%)	4/(50.0%)	5/(29.4%)	2/(40.0%)	22/(46.8%)
Early withdrawal	4/(100.0%)	7/(100.0%)	6/(100.0%)	8/(100.0%)	10/(58.8%)	5/(100.0%)	40/(85.1%)

Table 1: Patient disposition in the ARMY-1 study

Note: Percentages calculated using the total number of patients enrolled as the denominator * Includes 8 patients treated in the Step 2 of the study, all using the *"one-shot"* schedule

The majority of patients were early withdrawn from the study. The most frequently reported reason for withdrawal from study were disease progression and Investigator judgement (29.8% and 21.3%, respectively).

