8.2.3 Withdrawal of patients from therapy or assessment

Participation in the study is strictly voluntary and patients have the right to withdraw from the study at any time without explanation. This will not affect his/her rights for future medical care. Treatment should be discontinued also if this is in the best interest of the patient upon Investigator judgement and/or in case of any of the following:

- Non-compliance of the patient or investigator with the protocol
- Disease progression
- DLTs
- Infusion toxicities requiring permanent treatment discontinuation (see §8.4.7)
- Treatment-related grade 3 not haematological toxicity lasting more than 7 days occurring after the first cycle, excluding common complications of AML (in particular infections, bleedings, fatigue)
- Treatment-related grade \geq 4 not haematological toxicity occurring after the first cycle, excluding common complications of AML (in particular infections, bleedings, fatigue)
- Life threatening related Serious Adverse Event (SAE)
- Patient receives other treatment for AML (including HSCT)
- Occurrence of pregnancy

The Investigator is ultimately responsible for the safety and well-being of the patients and, if at any time during the study it is believed that the constraints of this protocol are detrimental to the patient's health, the patient may be withdrawn from the study.

Withdrawal of a patient must be notified to the study monitor, the reason(s) of withdrawal should be documented in the e-CRF and follow-up should be reported. For patients who withdraw from study, End of Study Visit has to be performed at the time of withdrawal.

If a patient prematurely terminates the study, data already collected will be used and analysed for the purpose of the study. In regard to biological samples already collected, in case of Informed Consent withdrawal, the patient may choose if samples not yet analysed, shall be analysed or destroyed.

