- Bone marrow aspirate for morphologic assessment on Visit 35 and Visit 37 only in patients showing peripheral blood labs consistent with CR/CRi/PR
- Recording of AEs and change in concomitant medications.

NOTES:

- To serve the best interest of the patients, for those achieving at least a partial remission, the Sponsor commits to consider providing MEN1112 to allow the prosecution of the infusions at the frequency recommended by the iDSMB on an individual basis and after discussion with the treating Investigator and the Medical Monitor. In this case, premedication and safety assessments will resemble those already described for study drug administration visits, unless differently advised by the iDSMB.
- During Follow-up Period, a time-frame of + 2 days each is allowed at any visit, however the scheduled time of the following visits should be maintained.

END OF STUDY

End of Study Visit (180 days after Visit 1/Day 1)

- Physical examination and vital signs
- PS evaluation
- Blood sampling for safety lab test including pregnancy test (if applicable)
- .

- Bone marrow aspirate for morphologic assessment,
- Recording of AEs and change in concomitant medications

NOTES:

- At the End of Study Visit, a time-frame of + 5 days is allowed.
- All patients shall undergo the End of Study Visit at the scheduled date or at the time of study withdrawal. Unscheduled assessments showing disease progression and leading to patient's withdrawal can replace the End of Study Visit provided that all assessment/procedures scheduled for this visit are completed.
- In case the patient is discontinued from the study within the treatment period, the End of Study Visit bone marrow aspirate is highly recommended to be performed.

GENERAL NOTES:

- For each safety lab test, blood sampling for PK (except for those to be collected at the end of infusion) and for vital signs, a window of +/- 5% of the required time interval is allowed.
- The total dose calculated for the first study drug administration can be applied also for the following ones providing that actual patient's weight is within ±10% of the weight measured prior to the first study drug administration; otherwise, the total dose to be given shall be calculated based on the weight measured at the corresponding visit.

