8.5.2.8 Monitoring and Recording of Adverse Events

The Investigator is responsible for the detection and documentation of events meeting the definition of AE, as provided in this protocol (see § 8.5.2.7.1).

All AEs, whether or not thought to be drug related, must be actively followed-up and recorded by the Investigator (or designee) in the source documents and in the appropriate section of the e-CRF throughout the whole study duration, starting from the Informed Consent signature to the End of Study Visit or 70 days after last study drug administration whichever occurs last.

NOTE: An AE will be considered as **'Treatment-Emergent Signs and Symptoms (TESS)'** if it occurs for the first time or if it worsens in terms of seriousness or severity after the first study drug intake (Visit 1).

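### For patients who withdraw within 70 days of the last dose, adverse events are recorded for longer than medication, so later AML therapy in that gap need not be recorded

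*Combined protocol and SAP*

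**What the plan says.** **Medication window.** Section 8.4.8: "the regular and occasional use of any concomitant medication has to be recorded starting from Screening until the End of Study Visit".

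**When that visit happens.** Section 8.5.1 schedules it 180 days after Day 1, but adds: "All patients shall undergo the End of Study Visit at the scheduled date or at the time of study withdrawal". Section 8.2.3 agrees: "For patients who withdraw from study, End of Study Visit has to be performed at the time of withdrawal".

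**AE window.** Section 8.5.2.8 records AEs "starting from the Informed Consent signature to the End of Study Visit or 70 days after last study drug administration whichever occurs last". In the flow chart (Section 2.2) the AE row carries a footnote with the same 70-day extension; the concomitant-medication row has no such footnote. Section 8.6.6 also requires a minimum of ten weeks of follow-up once treatment stops.

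**What counts as TESS.** An AE qualifies "if it occurs for the first time or if it worsens in terms of seriousness or severity after the first study drug intake". There is a start but no end, and no cut when another AML treatment begins.

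**Other AML therapy.** Section 8.4.8 bars active AML agents during the study, except hydroxyurea in the first cycle. Section 8.2.3 lists receipt of other AML treatment, transplantation included, among the reasons to stop MEN1112. No section requires the name or start date of such treatment to be recorded after withdrawal.

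**Tables.** Section 9.3.4 summarises AEs by grade, dose level, cycle, relationship and overall.

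**The concern.** The period in which medication recording has stopped but AE recording continues is the period in which other AML therapy is most likely to begin. Such therapy is not allowed on study, so it would normally start after withdrawal. Section 6.1 describes salvage chemotherapy, followed by transplantation where possible, as the general approach in relapsed or refractory disease. Toxicity from it would be new after the first dose of MEN1112 and would therefore be a TESS, counted at the patient's MEN1112 dose level.

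What is at stake is how the secondary safety tables can be read. Someone looking at overall, serious or grade 3 and higher TESS by dose level could not routinely tell which late events arose on another treatment. The exact start date of that treatment cannot be recovered at analysis if it was never collected.

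**Working it through.** **Plan's own figure.** From Table 1 (Section 6.2.4.1), early withdrawals by cohort sum to 4 + 7 + 6 + 8 + 10 + 5 = 40, and treated patients to 4 + 7 + 6 + 8 + 17 + 5 = 47. 40/47 = 85.1%, which matches the table.

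**Inputs**
- L = day of last dose (Day 36 if the schedule is completed; Section 8.4.5).
- E = day of the End of Study Visit: 1 + 180 = Day 181 on schedule, or the day of withdrawal (Sections 8.5.1 and 8.2.3).
- Medication recording ends on day E (Section 8.4.8).
- AE recording ends on the later of E and L + 70 (Section 8.5.2.8).

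**Formula.** Days with AE recording but no required medication record = max(E, L + 70) − E = max(0, L + 70 − E).

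| Days from last dose to End of Study Visit (E − L) | Gap (days) |
|---|---|
| 0 | 70 |
| 7 | 63 |
| 14 | 56 |
| 28 | 42 |
| 56 | 14 |
| 70 or more | 0 |

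**Who has no gap**
- Patients completing the schedule: 36 + 70 = Day 106, before Day 181.
- Patients who stop the drug but remain on study until at least 70 days after the last dose. The follow-up visits in Section 8.5.1 still record medication changes.
- Responders on continued infusions with an on-schedule final visit, provided the last dose is no later than 181 − 70 = Day 111. A last dose on Day 150 would give 150 + 70 − 181 = 39 days.

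**Illustration (dates assumed, not from the documents).** Last dose Day 15, withdrawal Day 22. Medication recording stops on Day 22 and AE recording runs to 15 + 70 = Day 85, a gap of 85 − 22 = 63 days.

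**What cannot be computed.** The documents give neither the time from last dose to withdrawal nor the number of patients who received other AML therapy. The number affected is therefore unknown.

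**Which tables are exposed.** The overall TESS tables take in every event in the gap. Related-event tables are less exposed, but not immune: Section 8.5.2.7.6 lets an event be graded possibly related even when other drugs could explain it, and counts both possible and unassessable events as adverse drug reactions. The DLT endpoint (Section 8.5.4.1) is confined to first-cycle events judged related to MEN1112, so it is largely outside the problem.

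**The case against.** The best defence is that the protocol keeps several routes to the missing information. Every AE gets a causality grade that weighs other drugs. For serious events, investigator and sponsor both assess causality, queries can be raised, and significant new information is due within 24 hours (Sections 8.6.1 and 8.6.2). Section 8.2.3 asks for the reason for withdrawal and for follow-up to be reported. These points stand as mitigation. They do not create a routine record of the drug and its start date, and the medication pages that the sponsor may consult have no required entries after the End of Study Visit.

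Stronger readings are tempting, and the documents do not support them:

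- *Late toxicity would have no trace of its cause.* The routes above say otherwise. What is missing is a required record.
- *The analysis could do nothing.* Events with onset after the withdrawal date can be tabulated separately without knowing the drug. That is a conservative cut; only the exact treatment start and the agent are lost.
- *About 85% of patients are affected.* Section 6.2.4.1 does say "The majority of patients were early withdrawn from the study", but the count covers withdrawal at any time and for any reason, in unclean data under the earlier schedule, which included open-ended monthly infusions. Only 29.8% left for progression. Eligibility also requires that no standard therapy is available or that the patient refuses it, so later therapy will not be universal.
- *The distortion grows with dose.* Early withdrawal was 100% in every cohort except 1.7 mg/kg (10/17, 58.8%), which shows no gradient.

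It is also fair to say that an overall TESS table that keeps every event is a defensible convention.

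**Conclusion.** The mismatch is in the text and no section closes it. Patients who withdraw less than 70 days after the last dose have up to 70 days of counted AEs without a required record of medication or subsequent AML therapy. All others have none, apart from responders dosed late. The effect falls on the all-causality TESS tables and, to a lesser degree, on events graded possibly related or unassessable.

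A reader might infer that the MTD is compromised. It is not, to any material extent: DLTs are first-cycle related events, although the iDSMB may also weigh Cycle 2 events and trends (Section 8.4.3.1).

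The gap length follows directly from the stated rules. Its practical weight rests on two things the documents do not give: how soon after the last dose patients withdraw, and how many then receive other AML therapy. This is a worthwhile and inexpensive correction to data collection, and no reason to doubt the primary endpoint.

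**What to change.** 1. **Section 8.4.8 and the flow chart.** Extend recording of concomitant medication, and of the name and start date of the first other AML treatment (transplantation included), to the AE end point in Section 8.5.2.8: the End of Study Visit or 70 days after the last dose, whichever is later. The gap then becomes zero for every patient.
2. **SAP.** Keep the overall TESS table. Add a supplementary table of TESS with onset before other AML treatment starts, plus later events judged related to MEN1112, and list the remaining later events separately. Section 9.5 has the SAP finalised before database lock, which leaves room for this.

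The cost is slightly more data entry for patients whom sites already follow for AEs, and one extra table with its listing. No treatment rule changes.
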